5.2.5.2 Contraception Guidelines for Female Subjects

A female enrolling in this study must meet ONE of the following contraceptive criteria from Screening until 30 days after the last dose of study drug:

1. Is postmenopausal at Screening

A postmenopausal state is defined as no menses for at least 1 year without an alternative medical cause. A high FSH level in the postmenopausal range may be used to confirm a postmenopausal state in women not using hormonal contraception or hormonal replacement therapy. However, a single FSH measurement is insufficient to establish a postmenopausal state without at least 1 year of amenorrhea.

2. Has documentation of one of the following performed before Screening:
 - a. Hysterectomy
 - b. Bilateral salpingectomy
 - c. Bilateral oophorectomy
3. Is sexually abstinent from penile-vaginal intercourse as her usual and preferred lifestyle (abstinent on a long-term and persistent basis) and agrees to remain abstinent from Screening until 30 days after the last dose of study drug
4. Any male sexual partner is vasectomized, and the absence of sperm has been confirmed
5. Agrees to use one of the following highly effective contraceptive methods, which must be in place from at least 1 month before Screening until 30 days after the last dose of study drug:
 - a. Combined hormonal contraception (containing estrogen and progestogen) associated with inhibition of ovulation: oral, intravaginal, or transdermal

Any hormonal contraception containing ethinyl estradiol must contain $\leq 35 \mu\text{g}$ ethinyl estradiol, is permitted only for subjects who would not be considered at high risk for thromboembolic or cardiovascular complications with estrogen use, and must be used simultaneously with a backup method of contraception. Acceptable backup methods of contraception include diaphragm with spermicide, cervical cap with spermicide, vaginal sponge with spermicide, and male or female condom with or without spermicide. Dosing of oral formulations of hormonal contraception containing ethinyl estradiol should be offset by approximately 10 hours from the evening dose of study drug. The Investigator may consult with the Medical Monitor regarding such individuals.
 - b. Progestogen-only hormonal contraception associated with inhibition of ovulation: oral, injectable, or implantable
 - c. IUD
 - d. IUS
 - e. Bilateral tubal occlusion

5.3 Screen Failures

Screen failures are defined as participants who consent to participate but are not subsequently randomized in the study. A minimal set of screen failure information is required to ensure transparent reporting of screen failure participants to meet the Consolidated Standards of Reporting Trials (CONSORT) publishing requirements and to respond to queries from regulatory authorities. Minimal information includes demography, screen failure details, and eligibility criteria.

If a subject fails to meet eligibility criteria during or at the end of the Run-in Period, the investigational site will schedule an abbreviated early termination visit to review AEs and concomitant medications and perform an abbreviated physical examination (preferably in the clinic, but also permissible via home visit).

Individuals who do not meet the following criteria for participation in the study may be rescreened according to the following guidelines:

- Individuals who do not meet the screening A4 inclusion criteria may be rescreened if their GC replacement dose is reduced and stable for ≥ 1 month. The Investigator will first consult with the Medical Monitor regarding such individuals. Any morning dose of GC medication should be taken after the screening blood draw to allow for an unimpeded assessment of hormones.
- Individuals on incompatible or excluded concomitant medications may be rescreened after an appropriate washout period (eg, 30 days or 5 half-lives, whichever is longer). The Investigator will first consult with the Medical Monitor regarding such individuals.
- Individuals who have an exclusionary laboratory value during the screening period may be retested before the start of the Treatment Period if the Investigator believes that the prior laboratory value is not consistent with the individual's overall clinical picture. The Investigator will first consult with the Medical Monitor regarding such individuals.

If appropriate, screening information transferred from Spruce Biosciences Study SPR001-204 to this study may be used to determine eligibility and fulfill screening requirements for this study.

6 STUDY INTERVENTION

6.1 Study Intervention Administration

6.1.1 Study Intervention Description

Tildacerfont is a small-molecule CRF₁ receptor antagonist.

Details about the physical, chemical, and pharmaceutical properties of tildacerfont are provided in the IB.

Study drug is defined as either tildacerfont or placebo.

Study treatment is defined more broadly as study drug or HC for stress dosing provided by the Sponsor.

6.1.2 Treatment Assignment, Dosing, and Administration

Subjects will use their own physician-prescribed supply of GCs as prescribed during the study, including during the Run-in Period.

Subjects will take placebo (during the Run-in Period) or assigned study drug (during the Treatment Period) orally each day between 6 PM and midnight, with an evening meal. The evening meal should contain approximately 25-50% fat content. Study drug may be consumed up to 30 minutes after completing the evening meal, if necessary.

During Part A (the first 12 weeks of the Treatment Period), subjects will be randomized in a 1:1:1:1 ratio to receive either placebo or tildacerfont at a dose of 50 mg QD, 100 mg QD, or 200 mg QD.

During Part B (the second 12 weeks of the Treatment Period) and Part C (the last 46 weeks of the Treatment Period), all subjects will receive active drug (tildacerfont).

- Subjects who were randomized to placebo in Part A will receive tildacerfont 100 mg QD at the beginning of Part B.
- Subjects who were randomized to tildacerfont 200 mg QD in Part A will continue to receive tildacerfont at 200 mg QD throughout Parts B and C.
- Based on A4 results from the Weeks 18 and 24 study visits, eligible subjects may undergo a tildacerfont dose escalation after each of these study visits. Specifically:
 - Subjects taking tildacerfont 50 mg QD will either continue to receive the same dose (if A4 ≤ULN) or be escalated to tildacerfont 100 mg QD (if A4 >ULN and the subject is tolerating his/her current tildacerfont dose)
 - Subjects taking tildacerfont 100 mg QD will either continue to receive the same dose (if A4 ≤ULN) or be escalated to tildacerfont 200 mg QD (if A4 >ULN and the subject is tolerating his/her current tildacerfont dose).
- At Week 30, all subjects will be escalated to 200 mg QD.

Immediately following the Weeks 18 and 24 visits, subjects will continue to take their previously assigned study drug until A4 laboratory results are received, the RTSM system determines the appropriate tildacerfont doses for the next portion of the study, and subjects receive their tildacerfont doses for the next portion of the study. Subjects will receive enough previously assigned study drug to last until they receive their appropriate tildacerfont dose for the next portion of the study. Subjects will either return to the clinic to pick up their study drug or will be shipped their study drug.

During the optional Open-Label Extension Period, subjects will continue to receive tildacerfont at 200 mg QD.

Only authorized study staff may dispense study drug. Sites will provide subjects with dosing instructions. The Sponsor will provide GC for periods of stress dosing. Sponsor-provided HC for stress dosing may be shipped directly to subjects.

Instructions for concomitant GC medication dosing are provided in [Section 6.5.1](#). Criteria for study drug discontinuation are provided in [Section 7.1](#).

6.2 Preparation/Handling/Storage/Accountability

6.2.1 Acquisition and Accountability

The Investigator is responsible for study treatment receipt and accountability, reconciliation, and record maintenance.

6.2.2 Formulation, Appearance, Packaging, and Labeling

The drug product is formulated as a tablet containing 50 mg and/or 200 mg of drug substance and the following inactive ingredients: lactose monohydrate, hydroxypropyl cellulose, sodium lauryl sulfate,

microcrystalline cellulose, croscarmellose sodium, colloidal silicon dioxide, magnesium stearate, and Opadry® yellow.

Placebo will be supplied as tablets that look identical to drug product but contain no drug substance.

Study drug tablets will be supplied in blister cards. [For the optional Open-Label Extension Period, study drug will be supplied either in blister card or in bottle pack.](#)

HC tablets for stress dosing will be supplied by the Sponsor in bottles.

6.2.3 Product Storage and Stability

All study treatment should be stored at room temperature, protected from light. Study treatment must be stored in a secure, environmentally controlled area that is monitored (manually or automatically) and accessible only to the Investigator and authorized study staff. Further details on the acceptable storage range for each study treatment are available in the study pharmacy manual.

6.3 Measures to Minimize Bias: Randomization and Blinding

All subjects will receive single-blinded placebo during the Run-in Period.

All subjects will be centrally randomized to study intervention in Part A and assigned to the appropriate dose of tildacerfont in Parts B and C using an RTSM system. Subjects will be randomized using the following strata: A4 \leq 4x ULN and A4 $>$ 4x ULN.

Investigators, subjects, and the Sponsor's contract research organization (CRO) will be blinded to assigned study intervention in Part A and to dose of tildacerfont in Parts B and C. To maintain the blind, all subjects will receive the same number of study drug tablets per dose, with the appropriate number of tildacerfont and/or placebo tablets for the assigned study intervention. The primary efficacy analysis is planned after all subjects have completed Week 18, at the end of the double-blind treatment period. The subject level blind will be maintained until the completion of the primary efficacy analyses. The Sponsor and CRO's will be unblinded at the time of the primary efficacy analysis (Part A--- Week 18), but Investigators, , and subjects will remain blinded to each subject's treatment assignment during Part B.

Emergency unblinding to a subject's treatment assignment should only occur when knowledge of the treatment assignment is necessary for immediate medical management of the subject. If emergency unblinding is required, the Investigator may use the code provided at the site initiation visit to access the subject's treatment assignment details via the RTSM system.

6.4 Study Intervention Compliance

Subjects will be asked to document study drug and background GC adherence in their electronic study diaries through Week 18 (see [Section 4.1](#)). Subjects will return study drug at each study visit to conduct accountability. The Investigator is responsible for ensuring that dosing is administered in compliance with the protocol.

Each subject's compliance information will be reviewed during the Run-in Period to determine eligibility for entering the Treatment Period and then will be reviewed on an ongoing basis for subjects who enter

the Treatment Period. Compliance information to be reviewed will include (but not be limited to), adherence to the subject's background GC regimen, adherence to the study drug regimen (including taking as instructed with food), adequate recording of data in the study diary.

6.5 Concomitant Therapy

Concomitant medication is any medication (including over-the-counter [OTC] medication, prescription medication, vaccines, vitamins, and supplements) that the subject is receiving at screening or receives during the study. All concomitant medications must be recorded, along with:

- Reason for use
- Dates of administration, including start and end dates
- Dosage information, including dose and frequency

All concomitant medications should be compared against the list of prohibited medications and the list of other medications of concern provided in [Section 13.1](#). Subjects should be instructed to contact the site immediately any time a new medication is required during the course of the study, including prescription and OTC medications, even those to be used for only a short period of time (e.g., antibiotics, cold and flu remedies, GI therapies, opioids or other pain relievers). The Medical Monitor should be contacted if there are any questions regarding concomitant or prior therapy.

6.5.1 Glucocorticoid Replacement Therapy

6.5.1.1 General Procedures for Glucocorticoids

Information to be collected at screening about a subject's current and historical GC therapy for the past year include the type(s) of GC, the regimen(s), reason(s) that the subject is/was on that particular GC regimen, and any GC stress dosing during the past year.

To be eligible for this study, subjects must be on a stable dose of GC replacement ≥ 15 mg/day and ≤ 60 mg/day in HCe (see [Section 6.5.1.2](#) for GC dose conversion to HCe) for ≥ 1 month before screening without any evidence of non-adherence to the GC regimen during this period (stress dosing is allowed). Changes in GC dosing are generally not permitted during this study except during Part C and in the case of stress dosing throughout the study (see [Section 6.5.1.5](#)). If a change in a subject's long-term GC regimen is clinically indicated outside of Part C (eg, the subject experiences symptoms of chronic adrenal insufficiency), study drug will be discontinued. Subjects who discontinue study drug for this reason should complete the early termination follow-up visit.

Subjects with the salt-wasting form of CAH must also be on a stable dose of mineralocorticoid replacement for ≥ 1 month before screening. A change to a subject's GC regimen during Part C could necessitate an adjustment to the subject's mineralocorticoid regimen. The adequacy of a subject's mineralocorticoid dose should be monitored and adjusted as needed to adequately maintain standing blood pressure, plasma renin levels, and electrolytes (serum potassium in particular) within acceptable ranges ([Speiser 2018](#)).

On the evenings before scheduled laboratory assessments, subjects should take their evening GC dose before 10 PM. On the mornings of scheduled laboratory assessments, subjects should delay taking any morning dose of GC medication until after the laboratory assessments have been completed. On all

other days during the study, subjects should take their GC medication at the usual time(s). Mineralocorticoid may be taken at any time of day, but its timing relative to laboratory assessments should be consistent throughout the study.

6.5.1.2 Glucocorticoid Dose in Hydrocortisone Equivalents

[Table 1](#) defines the potencies of various GCs relative to HC in treating CAH. These conversion factors will be used to determine whether a subject's daily GC dose satisfies study eligibility criteria and provide general guidelines for GC adjustment in Part C.

Note that fludrocortisone (a mineralocorticoid, not a GC) should not be converted to HCe or included in the calculation of a subject's total daily GC dose.

Table 1. Relative Potencies of Glucocorticoids in Hydrocortisone Equivalents (HCe)

Glucocorticoid	Potency in CAH (HCe)
Hydrocortisone	1
Prednisone	4 ¹
Prednisolone or methylprednisolone	5 ^{1,2}

¹[Zoorab 1998](#). ²[Clayton 2002](#). The protocol uses a 1:4 ratio for HC: prednisone and 1:5 for HC:prednisolone. However, transitioning from prednisolone to prednisone will require the closest approximation possible given the denomination of tablets available. Switching from 1mg prednisolone to 1mg prednisone is the closest approximation possible and therefore is not a protocol deviation.

6.5.1.3 Exclusion of Concomitant Dexamethasone

Subjects cannot be on dexamethasone during the study. Based on nonclinical and Phase 1 clinical data, tildacerfont is a moderate inhibitor of CYP3A4. Dexamethasone is primarily metabolized through CYP3A4, and Phase 2 clinical data have shown a potential for DDI between tildacerfont and dexamethasone. Thus, use of dexamethasone as GC therapy for CAH is not permitted during this dose-finding study.

Prior treatment with dexamethasone is allowed as long as the transition to an alternative GC (eg, HC, prednisone, prednisolone) has resulted in a stable dose of GC replacement for ≥ 1 month before screening. Prednisone/prednisolone and HC are metabolized through multiple pathways, with CYP3A4 comprising <18% of its metabolism ([Kovacs 2019](#), [Ohno 2008](#)). Based on static mechanistic modeling used to predict drug-drug interactions ([FDA 2000](#)), no clinically relevant increase in GC exposure is expected with prednisone/prednisolone or HC and tildacerfont. Phase 2 clinical data have shown a low likelihood of a DDI with tildacerfont.

6.5.1.4 Guidance for Changing Glucocorticoid Regimens in Part C and Optional Open-Label Extension Period

In Treatment Period Part C, subjects with A4 \leq ULN at Week 38 or Week 46 will begin to reduce their daily GC dose level in increments of approximately 5 mg/day HCe each time, per [Table 1](#).

In the optional Open-Label Extension Period, subjects will be eligible to adjust GC dose level at each visit. Subjects with A4 \leq ULN at any lab assessment will begin to reduce their daily GC dose level in increments of approximately 5 mg/day HCe each time, per [Table 1](#).

Per Investigator judgment, adjustments may also be made to the morning/afternoon/evening distribution of a subject's GC regimen without changing the total daily GC dose. Adjustments of GC dose may proceed so long as the adjustment is not precluded by an untoward clinical sign or symptom.

Changes to dosing frequency, ie, TID to BID, should be discussed with the Medical Monitor.

- Subjects with an A4 measurement of \leq ULN at Week 38, Week 46, or during the Open-Label Extension Period will begin to reduce their daily GC dose. Each reduction of the daily GC dose will be by approximately 5 mg/day HCe, down to a minimum of 15 mg/day in HCe (approximately physiologic replacement level). Reduction may stop at a GC level >15 mg/day in HCe based on Investigator judgment.
- If a subject has an A4 measurement of >1.25 x ULN, the subject's daily GC level should be increased by approximately 5 mg/day HCe each time.
- The daily GC level will generally remain unchanged for subjects with A4 levels $>$ ULN and ≤ 1.25 x ULN, unless a change in the GC dose level is clinically indicated (per Investigator judgment and discussion with the Medical Monitor).
- If a subject experiences a clinically significant episode of adrenal insufficiency due to undertreatment (as opposed to an acute stressor), the subject's daily GC dose should be increased by approximately 5 mg/day HCe and should not be reduced again to the GC dose level associated with adrenal insufficiency (per Investigator judgment and discussion with the Medical Monitor).

Sites will contact subjects by telephone within 2 weeks after each applicable study visit regarding GC dose adjustments. Sites will telephone subjects again 7 days after each GC dose adjustment to assess for the occurrence of AEs and the initiation of new concomitant medications.

6.5.1.5 Stress Dosing of Glucocorticoid

During times of clinically significant physical stress such as intercurrent illness with fever, surgical procedures, or significant trauma, subjects may take extra GC (in the form of HC) consistent with the "sick day guidelines" for prevention of adrenal crisis shown in [Table 2 \(Bornstein 2016\)](#). Sites may employ variations on these guidelines, consulting with the Medical Monitor, if possible, in non-urgent situations. The Sponsor will provide all subjects with oral HC for the purposes of stress dosing ([Section 6.2.2](#)). For subjects who are not taking HC as their background GC regimen, the stress dose of HC should be estimated based on the relative potencies of GCs outlined in [Table 1](#).

The stress doses recommended in [Table 2](#) are meant to *replace* a subject's usual daily GC dose; they are NOT taken *in addition* to the subject's usual daily GC dose. When taking the stress dose orally, the subject should take the entire stress dose using HC tablets from the bottle provided by the Sponsor. The subject's physician-prescribed GCs should be temporarily held during stress dosing and reinstated as soon as the stress dosing period ends.

While all GC stress doses should be entered into the EDC, changes to usual daily GC dose only need to be entered into EDC when there is a definitive long-term, chronic alteration in the usual daily GC dosing regimen.

Table 2. Sick Day Guidelines for Stress Dosing of Hydrocortisone

Condition	Stress Dosing of Hydrocortisone
Home management of fever >38 °C (>100.4 °F) or illness requiring bed rest, when requiring antibiotics for an infection, or before undergoing a minor outpatient procedure (eg, dental work)	
Approximately double the routine oral GC dose (and give as HC) until recovery (usually 2 to 3 days)For fever >39 °C (102.2 °F) only, approximately triple the routine oral GC dose (and give as HC) until recovery (usually 2 to 3 days)¹Increase consumption of electrolyte-containing fluids and simple and complex carbohydrates (El-Maouche 2018), as tolerated
Unable to tolerate oral medication due to gastroenteritis or trauma	
HC 100 mg IM or SC
Minor to moderate surgical stress	
HC 25 to 75 mg/24 hours (usually 1 to 2 days)
Major surgery with general anesthesia, trauma, or disease that requires intensive care	
HC 100 mg IV injection, followed by HC 200 mg/24 hours (via continuous IV infusion or 50 mg bolus every 6 hours IV or IM)Weight-appropriate continuous IV fluids with 5% dextrose and 0.2% or 0.45% NaClRapid tapering and switch to oral regimen depending on clinical state
Acute adrenal crisis	
HC 100 mg IV injection, followed by HC 200 mg/24 hours (via continuous infusion or 50 mg every 6 hours IV or IM), reduced to HC 100 mg/day the following dayRapid infusion of 1000 mL isotonic saline within the first hour or 5% glucose in isotonic saline, followed by continuous IV isotonic saline guided by individual patient needsFor hypoglycemia: 0.5 to 1 g/kg dextrose or 2 to 4 mL/kg of D25W (maximum single dose 25 g) infused slowly at rate of 2 to 3 mL/minCardiac monitoring: rapid tapering and switch to oral regimen depending on clinical state

Abbreviations: D25W, dextrose 25% in water; GC, glucocorticoid; HC, hydrocortisone; IM, intramuscular; IV, intravenous; SC, subcutaneous.

¹When tripling the routine oral GC dose, the HC stress dose should be rounded up to the next highest 10-mg HC tablet.

To prevent hypoglycemia, the subject should drink small amounts of clear sugar-containing liquids frequently and/or consume carbohydrates if the subject is able, glucose monitoring should be considered, and IV sodium and glucose replacement may be required ([Clayton 2002](#); [Merke and Bornstein 2005](#); [Keil 2010](#)).

Day-to-day physical or psychological stressors, such as a short-term strenuous activity or school examinations, do not require increased GC dosing ([Clayton 2002](#); [Crown & Lightman 2005](#); [Merke and Bornstein 2005](#)).

Subjects will maintain stress dosing until symptoms subside (or according to the clinical judgment of the treating physician), then return to their usual GC regimen. Any scheduled lab draws should be delayed until 5 to 7 days after subjects first return to their usual GC regimen. Any study visit delayed because of stress dosing will not be considered a protocol deviation. Extra unscheduled study visits for safety follow-up may be conducted in the interim.

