¹⁴ Subjects must be on a stable regimen of GC replacement ≥ 15 and ≤ 60 mg HCe per day throughout the Run-in Period, Part A, and Part B. Subjects will confirm whether their GC regimen was followed each day in a study diary. On the evenings before scheduled laboratory assessments, subjects should take their evening GC dose before 10 pm. On the mornings of scheduled laboratory assessments, subjects should delay taking any morning dose of GC medication until after the laboratory assessments have been completed.

¹⁵ In Part A, subjects will be randomized to tildacerfont 50 mg QD, tildacerfont 100 mg QD, tildacerfont 200 mg QD, or placebo.

¹⁶ In Parts B and C, all subjects will receive tildacerfont. Subjects who were randomized to placebo in Part A will receive tildacerfont 100 mg QD at the beginning of Part B. Subjects who were randomized to tildacerfont 200 mg QD in Part A will continue to receive tildacerfont 200 mg QD throughout Parts B and C. Based on A4 results from the Weeks 18 and 24 study visits, eligible subjects may undergo a tildacerfont dose escalation after each of these study visits. Specifically, subjects taking tildacerfont 50 mg QD will either continue to receive the same dose (if A4 \leq ULN) or be escalated to tildacerfont 100 mg QD (if A4 $>$ ULN and the subject is tolerating his/her current tildacerfont dose); subjects taking tildacerfont 100 mg QD will either continue to receive the same dose (if A4 \leq ULN) or be escalated to tildacerfont 200 mg QD (if A4 $>$ ULN and the subject is tolerating his/her current tildacerfont dose). At Week 30, all subjects will be escalated to 200 mg QD.

¹⁷ Either the subject will pick up study drug in the clinic or the study drug will be shipped directly to the subject. Study drug will be taken daily between 6 pm and midnight, with an evening meal. The evening meal should contain approximately 25-50% fat content. Study drug may be consumed up to 30 minutes after completing the evening meal, if necessary.

¹⁸ Immediately following each indicated study visit, subjects will continue to take their previously assigned study drug until subjects receive their tildacerfont doses for the next portion of the study.

¹⁹ IRT order assigned to specific participant. The shipment does not need to be accepted in IRT. Blister Cards will be assigned when the "Confirm A4 Value" action is recorded for Week 18 and week 24.

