- **Part C:** During the last 46 weeks of the Treatment Period, all subjects will be escalated to 200 mg QD, with periodic opportunities for GC adjustment for eligible subjects. Subjects and Investigators will continue to remain blinded to previous treatment in Part A and dose level of tildacerfont in Parts B and C.
 - Subjects with A4 ≤ULN at Week 38 or Week 46 will begin to reduce their daily GC dose level by increments of approximately 5 mg/day HCe each time, down to a minimum of 15 mg/day HCe (see [Section 6.5.1.4](#)).
- For subject's continuing into the optional Open-Label Extension Period
 - The Open-Label Extension Period will provide subjects with up to 240 weeks of treatment with tildacerfont 200 mg QD.
 - Subjects will be eligible to adjust GC dose level at each visit (see [Section 6.5.1.4](#)).
- A 30-day *Follow-up Period at EOT*
 - Subjects who do not continue to the Open-Label Extension Period upon completion of Treatment Period Part C will enter a 30-day Follow-up Period.
 - Upon completion of the Open-Label Extension Period, subjects will enter a 30-day Follow-up Period.
 - At the end of study treatment, subjects will maintain the GC regimen and mineralocorticoid regimen (as applicable) established during Part C until the 30-day follow-up visit unless the Investigator determines that the subject's clinical status necessitates a dosing change. After completion of the study, GC therapy will be managed at the discretion of the subject's treating physician.

Changes in GC dosing are generally not permitted during this study except after certain visits in Part C, the optional Open-Label Extension Period, and in the case of stress dosing throughout the study. During times of clinically significant physical stress such as intercurrent illness with fever, surgical procedures, or

significant trauma, stress dosing with extra GC (in the form of HC) for prevention of adrenal crisis will be allowed according to “sick day guidelines” (see [Section 6.5.1.5](#)).

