5.1 Eligibility Criteria

5.1.1 Inclusion Criteria

A subject must meet all of the following criteria to be eligible for this study:

1. Male and female subjects ≥ 18 years old at screening
2. Has a known childhood diagnosis of classic CAH due to 21-hydroxylase deficiency based on genetic mutation in *CYP21A2* and/or documented (at any time) elevated 17-OHP and currently treated with HC, HC acetate, prednisone, prednisolone, methylprednisolone (or a combination of the aforementioned GCs)
3. Has been on a stable, supraphysiologic dose of GC replacement (defined as ≥ 15 mg/day and ≤ 60 mg/day in HCe) for ≥ 1 month before screening
4. Has A4 $>$ ULN at both screening and Week 4 (measured before any AM GC dose) if daily GC dose < 30 mg OR has A4 $> 2.5 \times$ ULN at both screening and Week 4 (measured before any AM GC dose)
5. For subjects with the salt-wasting form of CAH, subject has been on a stable dose of mineralocorticoid replacement for ≥ 1 month before screening
6. Agrees to follow contraception guidelines ([Section 5.2.5](#)). Male subjects must also agree to refrain from donating sperm throughout the treatment period and for 90 days after the last dose of study drug.
7. Is able to understand all study procedures and risks involved and provides written informed consent indicating willingness to comply with all aspects of the protocol.

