11 COVID-19 RISK MITIGATION

11.1 Risk/Benefit Assessment in the Context of COVID-19 or Other Logistical Challenges

In general, the CAH patient population possesses a higher-than-average risk of serious complications from any infection or febrile illness because such conditions can lead to adrenal crises in CAH patients if they are not managed appropriately. The emergence of COVID-19 increases the overall infection risk in affected communities, including CAH patients who reside in those communities.

Participation in a clinical trial provides subjects with increased access to healthcare resources and reinforcement of appropriate practices during a time of increased infection risk. Study participants will have access to healthcare professionals on a more intensive schedule than in normal clinical practice for the management of CAH. The standard of care for a CAH patient with an infection or febrile illness is to increase the patient's GC dose to accommodate the additional stress and prevent an adrenal crisis (see

[Section 6.5.1.5](#)). The Sponsor will provide HC for stress dosing to all subjects during the study, starting at the beginning of the Run-in Period. Thus, study participants will have immediate access to supplemental GC in the event of COVID-19 or other infection.

The potential risks of a subject receiving tildacerfont and concomitantly developing COVID-19 have been considered. Tildacerfont is not expected to increase the risk of contracting a viral illness such as COVID-19 or to increase the risk of severe illness with COVID-19.

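### Table 2's surgical stress-dose range is not tied to the usual glucocorticoid dose it replaces, so above 25 mg/day HCe its lower part falls below the everyday dose

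*Protocol*

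**What the plan says.** Protocol Section 6.5.1.5 opens by saying that in clinically significant physical stress, with surgical procedures among the examples, "subjects may take extra GC (in the form of HC") in line with Table 2. Section 4.1.1 gives the purpose in similar words and also names surgery: "stress dosing with extra GC (in the form of HC) for prevention of adrenal crisis will be allowed".

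Section 6.5.1.5 then states that the Table 2 doses replace the usual daily dose and are not added to it. The subject's "physician-prescribed GCs should be temporarily held during stress dosing" and restarted afterwards.

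The row for minor to moderate surgical stress reads "HC 25 to 75 mg/24 hours (usually 1 to 2 days"). It does not mention the usual dose, and neither the table's single footnote nor SAP Section 5.2.3 sets a minimum in relation to it.

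The usual dose varies fourfold by design. Inclusion criterion 3 ("Has been on a stable, supraphysiologic dose of GC replacement") allows 15 to 60 mg/day HCe. Footnote 14 of Section 1.3.3 keeps the same limits, in "mg HCe per day throughout the Run-in Period, Part A, and Part B".

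**The concern.** A fixed range can serve as extra cover when it is added to the usual dose, or when its bottom lies above any dose the subject might already be taking. Here the usual dose is withdrawn, and the bottom of the range sits well inside the permitted span of usual doses. A subject on more than 25 mg/day HCe could be given a dose from the recommended range and receive less GC around an operation than on an ordinary day.

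What is at stake is the clarity of a safety instruction whose stated aim is to prevent adrenal crisis. No efficacy or analysis question depends on it. Subjects above 25 mg/day are expected: baseline HCe above 30 mg/day is a pre-defined subgroup in Protocol Section 9.4.8 and SAP Section 10.7. Neither document says how many there will be, or how many operations to expect.

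**Working it through.** There is no stated figure to reproduce. The check is arithmetic on the protocol's own doses.

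Inputs:
- Surgical row: 25 to 75 mg HC per 24 hours, a width of 75 − 25 = 50 mg (Table 2).
- Replacement rule: the usual dose is held, so the comparison is stress dose against usual dose, not against zero (Section 6.5.1.5).
- Usual dose D: 15 to 60 mg/day HCe (Section 5.1.1, criterion 3; Section 1.3.3, footnote 14).
- Conversion: prednisone × 4, prednisolone or methylprednisolone × 5 (Table 1).

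Formulas: bottom of range as a share of usual = 25/D; shortfall at the bottom = D − 25; share of the range below usual = (D − 25)/50; room above usual = 75 − D.

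| D (mg/day HCe) | 25/D | Shortfall at 25 mg | Share of range below D | 75 − D |
|---|---|---|---|---|
| 15 | 167% | none | 0% | 60 mg |
| 25 | 100% | none | 0% | 50 mg |
| 30 | 83% | 5 mg | 10% | 45 mg |
| 45 | 56% | 20 mg | 40% | 30 mg |
| 60 | 42% | 35 mg | 70% | 15 mg |

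The crossover is exactly 25 mg/day. Using Table 1, prednisolone 5 mg/day is 5 × 5 = 25 HCe, at the crossover; prednisone 7.5 mg/day is 7.5 × 4 = 30 HCe, already above it.

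The last column is positive at every entry dose, so a dose above the usual one is always available within the range.

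Is this peculiar to one row? The other rows give a multiple of the routine dose, 100 mg by injection, or 100 mg followed by 200 mg per 24 hours (reduced to 100 mg/day on the next day after a crisis). All exceed the 60 mg/day entry ceiling or scale above the usual dose. Only the minor-to-moderate surgical row reaches below a permitted entry dose.

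A floor must also work later in the study. Section 6.5.1.4 calls for increases of about 5 mg/day HCe whenever A4 exceeds 1.25 × ULN, in Part C and the extension, and states no ceiling. From 60 mg/day, three increases give 60 + 15 = 75 and four give 80. From 75 mg/day upwards the row contains no dose above the usual one, so a floor without a matching release of the 75 mg limit would leave no compliant dose.

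**The case against.** The strongest reply is that the opening sentence already governs the table. It speaks of additional GC, so a dose below the usual one is outside what the section authorises, and the reader is meant to take the part of the range above the subject's own dose. Because such a part exists for every entry dose, the row and the opening can both be satisfied. This largely stands: it would be too strong to call the two texts contradictory. It does not remove the point, because the row is what a site will consult and it presents 25 mg as a recommended dose without that condition.

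Next, the table is guidance. Sites may vary it, with the Medical Monitor consulted where possible in non-urgent cases, and SAP Section 5.2.3 places stress dosing under the physician's advice. This lowers the risk but sets no minimum.

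Third, the usual dose may not be the right yardstick. Entry doses are described as supraphysiologic and serve partly to suppress androgens. Section 6.5.1.4 puts approximately physiologic replacement at 15 mg/day, and 25 mg is 167% of that. Section 2.2.2 says physiologic doses may be enough to prevent adrenal insufficiency, although it does not address surgery. This also stands: the percentages above measure a mismatch in wording, not a clinical deficit.

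A reader might also set this row against the one for home illness and minor outpatient procedures, "Approximately double the routine oral GC dose (and give as HC) until recovery (usually 2 to 3 days"), and infer that the surgical row should double the dose too. The documents do not settle that. The home row concerns the routine oral dose, the surgical row states no route, and whether surgical cover should scale with the usual dose is a clinical choice. The comparison is not used here as support for the fix.

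**Conclusion.** The point holds as a minor safety clarification. For subjects above 25 mg/day HCe, the lower part of the recommended surgical range is below the dose they take every day, by 5 mg at 30 mg/day, 20 mg at 45 and 35 mg at 60. That does not fit the section's stated purpose.

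It rests on reading the row as written together with the replace-and-hold rule. It does not assume that clinicians would choose the bottom of the range.

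A reader might infer that the protocol instructs sites to under-dose surgical patients, or that subjects would be harmed. The documents support neither: a higher dose is always available within the range for any entry dose, and nothing shows 25 mg to be inadequate. The number affected is unknown. The subgroup above 30 mg/day gives no frequency, and entry at 30 mg/day or more requires A4 above 2.5 × ULN. No effect on the primary or any other endpoint is claimed.

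**What to change.** Add a footnote to the minor-to-moderate surgical row of Table 2: *Choose a 24-hour HC dose above the subject's usual daily GC dose in HCe (Table 1), and never below it; if the usual dose is 75 mg/day HCe or more, the 75 mg upper limit does not apply.*

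For usual doses of 30, 45 and 60 mg/day this leaves doses above 30, 45 and 60 mg respectively, up to 75 mg. Asking for a dose above the usual one matters, since a floor merely equal to it would allow no additional GC. The last clause covers the uncapped increases in Part C and the extension.

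Whether the floor should instead be twice the usual dose is a separate clinical decision for the sponsor.

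Cost: one footnote in the next amendment and a letter to sites. Table 2 already carries a dosing footnote. No new visits, data or analyses are needed.
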